4.2 Number of Sites and Subjects

A total of approximately 6 evaluable subjects will be enrolled in Cohort 1 and a total of approximately 215 subjects will be enrolled in Cohort 2. Approximately 45 study sites are planned in the US, Canada and Australia. During the conduct of the study, additional countries and/or sites may be added if necessary. Subjects will be adults (≥ 18 years of age) males or females with chronic hand eczema.

For Cohort 1, evaluable subjects are defined as those that:

- Complete 2 weeks of treatment

- Have PK results for all timepoints required at D1, D2, D15 and D16.

Unevaluable subjects in Cohort 1 may be replaced. Subjects in Cohort 2 will not be replaced.

4.3 Subject Participation

Phase 1 (Cohort 1)

Subject participation involves a minimum of 7 clinic visits including Screening, Baseline/Day 1, Day 2, Day 8, Day 15, Day 16 and Day 22. Subjects will be treated with investigational product (ARQ-252 cream 0.3% QD) for 2 weeks. The interval between the Screening and Baseline visits could be up to 4 weeks, therefore the anticipated maximum duration of subject participation is 7 weeks.

Phase 2b (Cohort 2)

Subject participation involves a minimum of 7 clinic visits including Screening, Baseline/Day 1, Week 2, Week 4, Week 8, Week 12 and Week 13. Subjects will be randomized to a treatment group and will be treated with investigational product for 12 weeks. The interval between the Screening and Baseline visits could be up to 4 weeks, therefore the anticipated maximum duration of subject participation is 17 weeks.

4.4 Randomization

Phase 1 (Cohort 1)

Phase 1 (Cohort 1) is open label and all enrolled subjects will be assigned treatment with ARQ-252 cream 0.3% QD at the Baseline visit. Subjects will be enrolled at the Baseline visit after the Investigator confirms that the subject meets all eligibility criteria listed in [Section 4.7](#). Enrollment will be documented by the completion of the Enrollment Notification Form.

Phase 2b (Cohort 2)

Phase 2b (Cohort 2) is randomized. Randomization will take place at the Baseline visit after the Investigator confirms that the subject meets all eligibility criteria listed in [Section 4.7](#). Subjects will be randomly assigned to apply ARQ-252 0.3% QD, ARQ-252 0.3% BID, ARQ-252 0.1% QD, vehicle cream QD or vehicle cream BID by an interactive response technology system (IRT).

Assignment of treatment arm will be made at a 2:2:1:1:1 ratio and stratified by study site and IGA at baseline according to a computer-generated randomization list. Kits containing tubes of investigational product will be assigned to each subject by the IRT system. A subject may receive more than one kit for the treatment period. The kits and tubes will be labeled with a unique number, in a blinded manner.

4.5 Numbering of Subjects

Phase 1 (Cohort 1)

All subjects who sign informed consent will be assigned a unique six-digit subject ID number by the site. The first three digits will correspond to the site number (assigned by the Sponsor) and the next three digits correspond to the sequential order in which the subject is screened for the study.

Phase 2b (Cohort 2)

All subjects who sign informed consent will be assigned a unique six-digit subject ID number by the IRT system. The first three digits correspond to the site number (assigned by the Sponsor), the next three digits correspond to the sequential order in which the subject is screened for the study.

The clinical site is responsible for maintaining a current log of subject ID number assignments and the kit number assigned to that subject. The subject ID number is required to be entered on all clinical study documentation (e.g., case report forms, labeling of clinical materials and sample containers, investigational product accountability logs, etc.).

4.6 Blinding

Phase 1 (Cohort 1) is not blinded.

Phase 2b (Cohort 2) is double-blinded, therefore neither the subjects nor the Investigator and clinical personnel will be aware of which investigational product (ARQ-252 0.1% cream, ARQ-252 0.3% cream or vehicle cream) an individual subject receives. The subjects, Investigator and clinical personnel will be aware of whether IP is to be applied QD (once daily) or BID (twice daily).

4.6.1 Breaking Treatment Codes

Phase 2b (Cohort 2)

In the event of a medical emergency where breaking the blind is required to provide medical care to the subject, the Investigator may obtain treatment assignment directly from the IRT system for that subject. Refer to the current version of the IRT plan for details on unblinding. Treatment assignment should, however, remain blinded unless the assignment knowledge is necessary to determine subject emergency medical care. The rationale for unblinding must be clearly explained in source documentation and on the CRF, along with the date on which the treatment assignment was obtained. The Investigator is requested to contact the Sponsor promptly in the event of any treatment unblinding.

Blinding of study treatment is critical to the integrity of this clinical trial and therefore, if a subject's treatment assignment is disclosed to the Investigator, the subject will have the study treatment discontinued. All subjects will be followed until study completion unless consent to do so is specifically withdrawn by the subject.

4.7 Selection of Study Population

4.7.1 Inclusion Criteria

Subjects must fulfill all of the following inclusion criteria to be eligible for participation in the study:

1. Participants legally competent to sign and give informed consent.
2. Males and females 18 years of age and older (inclusive) at the time of consent.
3. Clinical diagnosis of chronic hand eczema, defined as hand eczema persistent for more than 3 months, or returned twice or more within the last 12 months (Diepgen 2009). Generally stable disease for 6 weeks. Both irritant and non-irritant etiologic forms are allowed. All morphologic types are allowed, e.g., vesicular/dyshidrotic, hyperkeratotic, nummular, and other types.
4. An Investigator's Global Assessment of disease severity (IGA) of at least Mild ('2') at Baseline (Visit 2). (In Cohort 2, subjects with IGA of 'Mild' will be limited to 20% of total enrollment, and subjects with IGA of 'Severe' subjects will also be limited to 20% of total enrollment).
5. Chronic hand eczema involving at least 0.3% body surface area total (i.e., approximately a third of one handprint) lesions on both hands added together at Baseline (Visit 2).
6. Female subjects of childbearing potential (FOCBP) must have a negative serum pregnancy test at Screening and negative urine pregnancy test at Baseline (Visit 2). For FOCBP involved in any sexual intercourse that could lead to pregnancy: the subject must agree to use a highly effective contraceptive method for at least 4 weeks prior to Day 1. Additionally, from Day 1 until at least 4 weeks after the last investigational product administration, these subjects must agree to use at least 1 highly effective contraceptive method in addition to 1 barrier method according to Contraception Requirements (Figure 1).
7. Females of non-childbearing potential must either be post-menopausal with spontaneous amenorrhea for at least 12 months (post-menopausal status will be confirmed with FSH testing) or have undergone surgical sterilization (permanent sterilization methods include hysterectomy, bilateral oophorectomy, hysteroscopic sterilization, or bilateral salpingectomy) according to Contraception Requirements (Figure 1).
8. Males, if engaging in sexual intercourse with a female who is pregnant or a female of childbearing potential, must agree to use a condom every time during the study and every time subsequently until 4 weeks after the last investigational product administration.
9. Males must agree not to donate sperm from the first dose of investigational product until 4 weeks after the last investigational product administration.
10. Subjects in good health as judged by the Investigator, based on medical history, physical examination, 12-lead electrocardiogram (ECG), serum chemistry labs, hematology values, and urinalysis.
11. Subjects are considered reliable and capable of adhering to the Protocol and visit schedule, according to the judgment of the Investigator.

4.7.2 Exclusion Criteria

Subjects who meet any of the following exclusion criteria will be excluded from participation in this study:

1. Concurrent skin diseases on the hands which, in the opinion of the Investigator, could confound the study (e.g., tinea manuum).
2. Active skin diseases not on the hands such as atopic dermatitis or psoriasis requiring medical treatment that could significantly affect hand eczema, in the Investigator's opinion.
3. Subjects with any presence or history of psoriasis.
4. History of a positive patch test with continued exposure to allergen. If, in the opinion of the Investigator, there is any suspected allergic hand eczema with continued exposure to allergen, subject must undergo diagnostic patch testing to determine if they meet entry criteria prior to Baseline (Visit 2).
5. Subjects who cannot discontinue systemic and/or topical therapies for the treatment of chronic hand eczema prior to Baseline (Visit 2) and during the study according to Excluded Medications and Treatments (Table 2), (i.e., immunosuppressive drugs, immunomodulating drugs, retinoids, or corticosteroids).
6. Psoralen ultraviolet A (PUVA) or ultraviolet B (UVB) therapy on the hands within 4 weeks prior to Baseline (Visit 2).
7. Cutaneously applied treatment with immunomodulators (e.g., phosphodiesterase-4 (PDE-4) inhibitors, pimecrolimus, tacrolimus), topical urea moisturizers, topical antibiotics, or low or mid potency topical corticosteroids on the hands or elsewhere within 1 week prior to Baseline (Visit 2). Cutaneously applied treatment with high potency topical corticosteroids on the hands or elsewhere within 2 weeks prior to Baseline (Visit 2).
8. Subjects that have significant active systemic or localized infection, including known actively infected eczema or have had any infection that required oral or intravenous administration of antibiotics, antifungal or antiviral agents within 2 weeks prior to Baseline (Visit 2).
9. Other cutaneously applied therapy on the hands (except for the use of subject's own non-urea and non-salicylic acid emollients) within 1 week prior to Baseline (Visit 2).
10. Subjects who are unwilling to refrain from using a tanning bed or other LEDs as well as outdoor tanning or excessive sun exposure for 4 weeks prior to Baseline (Visit 2) and during the study.
11. Subjects with a history of chronic alcohol or drug abuse within 6 months prior to Baseline (Visit 2).
12. Current or a history of cancer within 5 years with the exception of fully treated skin basal cell carcinoma, cutaneous squamous cell carcinoma or carcinoma in situ of the cervix.
13. Subjects that have received live vaccine therapy less than 4 weeks prior to Baseline (Visit 2), immunosuppressive drugs less than 4 weeks prior to Baseline (Visit 2), or have known infection with mycobacterium tuberculosis, hepatitis B or C, or HIV, or have a diagnosis of an immunodeficiency disorder.

14. Subject had a major surgery within 4 weeks prior to Baseline (Visit 2) or has a major surgery planned during the study.
15. Known or suspected:
 - severe renal insufficiency or severe hepatic disorders
 - hypersensitivity to component(s) of the investigational product which include SHR0302, butylated hydroxytoluene (BHT), benzyl alcohol, dimethyl sulfoxide, cyclomethicone, dimethicone (350 cst), ST-Elastomer 10, water, propylene glycol, polyethylene glycol 200, Pemulen TR1, Carbopol 974P, ethylenediaminetetraacetic acid, trolamine and D-limonene.
16. Pregnant or lactating women or women planning to become pregnant during the study and / or within 28 days following the last dose of investigational product.
17. Subjects who cannot discontinue the use of strong systemic Cytochrome P-450 3A4 inducers e.g., efavirenz, nevirapine, glucocorticoids, barbiturates (including phenobarbital), phenytoin, rifampin and carbamazepine for 2 weeks prior to Baseline (Visit 2) and during the study period.
18. Subjects who cannot discontinue the use of strong systemic Cytochrome P-450 3A4 inhibitors e.g., indinavir, nelfinavir, ritonavir, clarithromycin, itraconazole, ketoconazole, fluconazole, nefazodone, saquinavir, suboxone and telithromycin for 2 weeks prior to Baseline (Visit 2) and during the study period.
19. Subjects with any serious medical condition or clinically significant laboratory, ECG, vital signs or physical examination abnormality that would prevent study participation or place the subject at significant risk, as judged by the Investigator.

4.8 Removal of Subjects from Investigational Product

A subject may discontinue investigational product for any of the following reasons:

- Occurrence of any medical condition or circumstance that, in the opinion of the Investigator, does not allow the subject to adhere to the requirements for investigational product as per the protocol.
- Adverse Events as described in [Section 4.10](#). The Investigator must follow the subject until the AE resolves or satisfactorily stabilizes.
- Treatment must be discontinued immediately in the event of a female subject's pregnancy.
- Subject's decision to withdraw from investigational product.
- Requirement for use of prohibited concomitant medication after consultation with the Sponsor and Medical Monitor.
- Subject's repeated failure to comply with protocol requirements or study related procedures.

4.9 Removal of Subjects from the Study

A subject may be removed from study participation for any of the following reasons:

- Subject death.
- Subject's decision to withdraw from study.
- Subject is lost to follow-up. A subject will be considered lost to follow-up after three phone and three email attempts and documentation of a certified letter sent to the subject's address.
- Termination of the study by the Sponsor, FDA, or other regulatory authorities.

4.10 Treatment Stopping Rules

If a subject has non-cutaneous adverse events of concern, clinically significant laboratory values or any condition that the Investigator determines could possibly be related to the investigational product, the Investigator should immediately contact the Medical Monitor to discuss if the subject should be discontinued from treatment with investigational product.

Treatment for any individual subject will be discontinued if the subject experiences:

- A serious adverse event (SAE) or a clinically significant non-serious AE which in the opinion of the Principal Investigator or Medical Monitor warrants discontinuation from the study for that subject's well-being.
- A treatment-emergent severe (Grade 3 or higher) laboratory abnormality (confirmed by repeat sample).
- A severe infection (Grade 3 or higher)
- An Ischemic or thromboembolic cardiovascular event (regardless of Grade)
- Any other adverse event that represents an unacceptable risk to the subject (e.g., Grade 3 or higher)

As noted above, study treatment must be discontinued immediately in the event of a female subject's pregnancy.

Treatment should be interrupted:

- If a subject develops an application site reaction with the clinical appearance of an 'irritation reaction', and with a severity of a Dermal Response Score of 5 (erythema, edema and papules) or greater on the scale of Berger and Bowman, treatment should be interrupted for up to one week and may then be resumed if the reaction has, in the opinion of the Investigator, adequately resolved.

Treatment should be discontinued:

- If the application site reaction reoccurs, treatment should be discontinued permanently, and the subject followed until the reaction resolves.

For cases of suspected allergic contact dermatitis, the Medical Monitor and Sponsor should be notified and there should be discussion about performing patch testing to further evaluate. Patch testing is encouraged in such cases.

Phase 2b (Cohort 2)

In the event of a medical emergency where unblinding is required to provide medical care to the subject, refer to the most current IRT plan and Breaking Treatment Codes ([Section 4.6.1](#)). Contact the Medical Monitor and the Sponsor promptly.

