- ^e Subjects will complete the WI-NRS pruritis assessment and NRS Pain assessment in the clinic during Screening and then daily at home from the Baseline/Day 1 visit until the Week 13 visit. QOLHEQ = Quality of Life in Hand Eczema Questionnaire will be completed at each visit.
- ^f Assessment of nail dystrophy including Baseline identification of the nail with the worst dystrophy and measurement of the millimeters of normal appearing nail distal to the cuticle post Baseline. Sites participating in optional photography will obtain photos of nail with the worst dystrophy at Baseline/Day 1 and at subsequent visits. See [Section 5.2.7](#) for details.
- ^g Local tolerability assessments to be recorded prior to IP application for the Investigator assessment of skin irritation (Berger and Bowman skin irritation score) and 10-15 minutes post IP application for the subject's '0-3' burning/stinging assessment. **Note for investigator tolerability assessments: reactions at the site of IP application, which may occur post-Baseline, should be differentiated from the preexisting inflammation associated with the subject's chronic hand eczema.**
- ^h Photography will be performed at selected investigational sites. Photography will be optional. All efforts will be made to de-identify the subjects. Sites participating in optional photography will obtain photos of nail with the worst dystrophy at Baseline/Day 1 and at subsequent visits.
- ⁱ A serum pregnancy test will be administered to all females of childbearing potential at Screening. A urine pregnancy test will be administered at Baseline, Weeks 4, 8, 12 and 13. A negative result is required for continued participation in the study, and results must be available prior to dispensing of investigational product.
- ^j FSH will be performed (if indicated) at Screening to confirm post-menopausal status.
- ^k PK assessments will be collected from all subjects at Days 1, 29 and 85. The draws will be pre-dose IP application in the clinic.
- ^l Subjects to apply assigned IP in clinic at these visits. The time of application will be documented.
- ^m Kits will be dispensed at Baseline, Weeks 2, 4 and 8. Dispensing at Week 12 requires approval from the Medical Monitor. See IP Handling Manual for details.

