5.5 Early Termination Visit

If a subject is withdrawn or wishes to exit the study prior to the final study visit, an early termination visit will be scheduled. This visit should include the procedures and assessments that would be performed at the final study visit for either Cohort 1 or Cohort 2 ([Section 1.3](#)).

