5.8 Reporting Pregnancy

During the study, all subjects should be instructed to contact the Investigator immediately if they suspect they might be pregnant (e.g., missed or late menstrual period). If pregnancy is confirmed, Investigational Product must be discontinued immediately, the subject should be referred to an obstetrician experienced in reproductive toxicity for evaluation and counseling, and the subject should be followed until conclusion of the pregnancy. Subject may be required to sign a separate informed consent form to obtain pregnancy follow-up information, per local requirements.

The Investigator is responsible for reporting all available pregnancy information on the pregnancy report and submitting to the Medical Monitor within 24 hours of becoming aware of the event, although pregnancy itself is not considered an AE. Follow-up information detailing the outcome of the pregnancy and the health of the newborn should be reported as it becomes available. Any pregnancy resulting in a congenital abnormality or birth defect of the newborn, or neonatal death occurring within 30 days of the birth must be reported as a SAE, regardless of causality. Any infant death that occurs after the 30 day reporting period that the Investigator suspects is related to Investigational Product must also be reported as an SAE.

Partner pregnancies of a male subject will be reported.

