##### Phase 2b (Cohort 2):

The primary endpoint of Cohort 2 is:

- The rate of an Investigator Global Assessment (IGA) score of “clear” or “almost clear” at Week 12

The primary estimand for the primary efficacy endpoint of this study is the odds of achieving IGA score of “clear” or “almost clear” (i.e., IGA success) at 12 weeks; that is, the ratio of the odds of achieving IGA success at 12 weeks ARQ-252 relative to the odds of success at 12 weeks of using a matching vehicle cream. In the course of the 12-week randomized treatment period, subjects may be exposed to possible known or unknown intercurrent events that could possibly affect the estimand, such as treatment discontinuation due to a specific adverse effect or perhaps a lack of effect. The “Treatment Policy Strategy” has been adopted for handling all known or unknown intercurrent events in this study. To this end, the ITT principle will serve as the analytical basis for interpreting the estimand. In other words, the odds ratio of achieving IGA success for ARQ-252 relative to vehicle at 12 weeks will be evaluated regardless of the occurrence of any such intercurrent event. This estimand shall be estimated using the Cochran-Mantel-Haenszel (CMH) approach and applies to the following treatment comparisons:

- ARQ-252 cream 0.3% BID versus vehicle cream (all dose frequencies)
- ARQ-252 cream 0.3% QD versus vehicle cream (all dose frequencies)
- ARQ-252 cream 0.1% QD versus vehicle cream (all dose frequencies)
- ARQ-252 cream (all strengths and dose frequencies) versus vehicle cream (all dose frequencies)
- ARQ-252 cream 0.3% (all dose frequencies) versus vehicle cream (all dose frequencies)

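### Two phrases in the protocol read a product stop as a study exit, so some Week 12 IGA values that the treatment-policy estimand needs may never be collected

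*Protocol*

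**What the plan says.** The protocol separates stopping product from leaving the study.

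- Protocol 4.8: "A subject may discontinue investigational product for any of the following reasons". The reasons include adverse events, pregnancy, prohibited medication and repeated non-compliance.
- Protocol 4.9: "A subject may be removed from study participation for any of the following reasons". The reasons are death, the subject's own decision, loss to follow-up, and termination of the study.

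Three places do not fit that separation.

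- Protocol 4.10, first bullet. The lead-in is about stopping treatment, but the bullet is triggered by an event which "in the opinion of the Principal Investigator or Medical Monitor warrants discontinuation from the study".
- Protocol 1.3, Cohort 2 footnote i and Cohort 1 footnote g, both copied into the SAP schedule tables: "A negative result is required for continued participation in the study, and results must be available prior to dispensing of investigational product". Protocol 5.8 stops product only: "If pregnancy is confirmed, Investigational Product must be discontinued immediately".
- SAP Table 14.1.1. Its reasons for premature discontinuation from the study include adverse event, pregnancy, non-compliance, protocol violation and physician decision. None of these is a 4.9 reason.

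On follow-up, Protocol 4.6.1 says "All subjects will be followed until study completion unless consent to do so is specifically withdrawn by the subject". The sentence recurs only in SAP 3.6, and both sections concern unblinding. On exit, Protocol 5.5 says "If a subject is withdrawn or wishes to exit the study prior to the final study visit, an early termination visit will be scheduled".

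For the primary endpoint, SAP 2.2.1.1 says that the treatment policy strategy "has been adopted for handling all known or unknown intercurrent events in this study".

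**The concern.** A treatment-policy estimand asks for the Week 12 IGA of every randomized subject, including those who stopped cream. Collecting it depends on sites keeping those subjects on the visit schedule. The sections a site would consult when a subject stops (4.8, 4.9, 4.10, 5.5) contain no instruction to continue visits, and two phrases point to an exit. If a site follows them, Week 12 is imputed by a model that cannot tell whether the subject was still on cream. A value that was never collected cannot be recovered at analysis.

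**Working it through.** The plan states no figure on this point, so there is none to reproduce. The check has three parts.

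**1. What happens to the Week 12 value after an exit**

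- The early termination visit repeats the final-visit procedures, which include IGA (Protocol 5.5 and 1.3).
- That IGA can stand in for Week 12 only if it falls on Days 71-90 and no scheduled value exists (SAP 6.1.5.1, Table 4). Before Day 71 it can count only for an earlier visit.
- A missing Week 12 IGA is imputed from earlier IGA, treatment group and pooled site group (SAP 6.1.4). There is no on/off-treatment term.
- The Cohort 2 sensitivity analyses use nonimputed data (SAP 8.1.2), so they omit these subjects and cannot show the effect.
- One partial remedy exists. IGA is collected at unscheduled visits, including adverse event follow-up (Protocol 5.6), and such a value on Days 71-90 may serve as Week 12.

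**2. Size**

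Error in the active-minus-vehicle difference = stopping rate x share with no Week 12 value x (imputed response - true off-cream response).

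- *Stopping rate.* Not given for the cream. In the oral study, adverse event discontinuations through Week 12 were 1 or fewer per group, with active groups of 23 to 45 (Protocol 2.3.2). Upper bounds are 1/45 = 2.2% and 1/23 = 4.3%; times 61 subjects that is 1.3 to 2.7, or about 1 to 3. An upper scenario of 10% matches the planned dropout (Protocol 6.1.1) and the oral study's all-cause non-completion, (194 - 174)/194 = 10.3%.
- *Share without a Week 12 value.* Assuming exits spread evenly over 85 days, 70/85 = 0.82.
- *Imputed response.* Taken from a simulation of the planned imputation: latent IGA with SD 1, adjacent-visit correlation 0.7, baseline mean 3, improvement proportional to the square root of time, Week 12 response 45% active (n=61) and 15% pooled vehicle (n=62), predictive mean matching with 5 donors, site omitted. The result is 43% if stoppers match their arm before stopping, 35% if half a grade worse and 28% if one grade worse. Varying the correlation from 0.5 to 0.85 takes the lowest case down to 21%. The ceiling is the arm's own 45%.
- *Off-cream response.* Not given; 15% and 30% are assumed.

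Error in percentage points (positive = overstatement):

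| Stopping rate | Off-cream response | Imputed 45% | 43% | 35% | 28% | 21% |
|---|---|---|---|---|---|---|
| 2.2% | 15% | 0.5 | 0.5 | 0.4 | 0.2 | 0.1 |
| 4.3% | 15% | 1.1 | 1.0 | 0.7 | 0.5 | 0.2 |
| 10% | 15% | 2.5 | 2.3 | 1.6 | 1.1 | 0.5 |
| 2.2% | 30% | 0.3 | 0.2 | 0.1 | 0.0 | -0.2 |
| 4.3% | 30% | 0.5 | 0.5 | 0.2 | -0.1 | -0.3 |
| 10% | 30% | 1.2 | 1.1 | 0.4 | -0.2 | -0.7 |

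For example, 0.10 x 0.82 x (45 - 15) = 2.5 and 0.10 x 0.82 x (21 - 30) = -0.7.

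**3. Significance**

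The SAP compares each active arm with pooled vehicle (55 against 56), at two-sided 0.10, planning on 45% against 15%. For a chi-square test without continuity correction, power = Phi((difference - 1.645 x SE0)/SE1). At 45%, SE0 = 0.0869 and SE1 = 0.0823, so (0.30 - 0.1429)/0.0823 = 1.91 and power is 97.2%. At 44% it is 96.4%.

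**The case against.** The strongest reply is that the operative rules already agree. Section 4.10 is headed as treatment stopping rules, and its bullets sit under a lead-in about stopping treatment. Section 4.9 admits no adverse event or pregnancy reason. The pregnancy footnotes concern testing before product is dispensed, and the 4.6.1 sentence is worded for all subjects. Harm requires a site to read one bullet or footnote against 4.9.

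Most of this stands. It is why the point concerns conflicting wording, not a prescribed loss of data. It does not dispose of the point, because the SAP's own disposition shell expects adverse event, pregnancy and non-compliance as study exits, and the general sentence is neither repeated nor cross-referenced where product stops are described.

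A second reply is that the figures are generous. That also stands.

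- They charge every product stop to the wording, although only the first 4.10 bullet and the pregnancy footnotes carry it. If half the losses are due to the wording, every figure halves.
- They give no credit for IGA collected at unscheduled visits.
- Part of the 10% scenario is consent withdrawal or loss to follow-up, which no wording prevents.
- The oral rate is an upper bound from another route and population. Protocol 2.4.2 expects lower risk with topical delivery, though application-site reactions are not represented in the oral figure.

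**Conclusion.** The inconsistency is in the text and worth correcting, at the level of a cheap improvement to consider. A reader might infer that the protocol removes subjects who stop cream, or that the primary result will be materially inflated. The documents support neither. Section 4.9 keeps these subjects in by default, and the stopping rates and off-cream responses behind any bias are assumptions.

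On those assumptions the error runs from -0.3 to 1.1 points at 2.2-4.3% stopping, so roughly 0 to 1 point of the planned 30. At 10% stopping it runs from about -0.7 to 2.5 points. The direction is usually overstatement, but it reverses when stoppers were doing poorly and would still have responded reasonably well off cream. A change in significance is unlikely. The reason to act is that the wording is easily settled beforehand.

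**What to change.** Carry these edits in the next amendment; they do not justify a standalone one.

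1. Protocol 4.10, first bullet: refer to *discontinuation of investigational product* instead of discontinuation from the study. Under its lead-in the bullet becomes somewhat circular, but the trigger remains the clinical judgement of the investigator or Medical Monitor.
2. Protocol 1.3 footnotes i (Cohort 2) and g (Cohort 1), and their copies under SAP Tables 2 and 1: make the negative pregnancy test a condition of *continued treatment with investigational product*. Footnote g has no bearing on the Cohort 2 estimand and is changed for consistency.
3. Protocol 4.8: state that Cohort 2 subjects who stop investigational product continue scheduled visits, including the Week 12 IGA, unless they withdraw consent for follow-up.

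Optionally, add a block to SAP Table 14.1.1 for discontinuation of product. SAP 9.1 already separates drug from study discontinuation for treatment-emergent events.

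The cost is a minor wording change that needs IRB approval (Protocol 7.6) across about 45 sites in three countries (Protocol 4.2), and some off-treatment attendance at visits already on the schedule. No visit is added and the sample size is unchanged.
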